2.0 Abbreviations

3D	Three-dimensional (environments)
BCCH	British Columbia Children's Hospital
CLS	Child Life (Specialists)
IPD	Interpupillary Distance
LoS	Length of (Hospital) Stay
MRI	Magnetic Resonance Imaging
PDSA	Plan-Do-Study-Act cycle
RA	Research Assistant
Short-STAI	Short State-Trait Anxiety Inventory
TCPS-2	Tri-Council Policy Statement
TRL	Technology Readiness Level
VR	Virtual Reality

3.0 Introduction

Operational Context

Over 4500 patients undergo magnetic resonance imaging (MRI) at BC Children's Hospital (BCCH) each year (**Table 1**). In 2017/18, the waitlist for sedated cases reached a significant point where some patients were forecasted to endure a wait of up to two years for their scheduled appointment. To address this, the Hospital launched a coordinated strategy that included increased operational capacity and funding for clinical and support services. Child Life Specialists (CLS), who are specially trained individuals that work with patients and families to help prepare patients for the MRI procedure, were amongst these resources. CLS are considered a key factor in enabling some patients to undergo imaging without the use of sedation, where otherwise it may have been indicated due to pre-procedural anxiety and high probability of non-compliant behaviors. While the Hospital has invested efforts and resources in improving access to CLS, capacity limitations exist, and there are socioeconomic costs of only having this support available on-site at BCCH. The Project Team intends to develop a standardized preparatory adjunct delivered using virtual reality (VR) technology, and explore the effectiveness of this tool. Ultimately, our goal is to explore the potential for this adjunct to complement the existing efforts of the Medical Imaging Department and Child Life Specialists to improve access, quality, efficiency, and patient experience at BCCH. A core component of this project is to also assess the economic impacts of this solution.

Table 1. Magnetic Resonance Imaging statistics from BC Children's Hospital (BCCH) Child Life Department, Fiscal Year 2018/2019.

	Q1	Q2	Q3	Q4 (as of Feb 22, 2019)
Non-Sedated	644	576	644	530
Sedated	443	475	483	487
TOTAL	1,087	1,051	1,127	1,017

Pre-procedural anxiety and non-compliance

Fifty percent of pediatric patients experience elevated anxiety and distress prior to new medical procedures.¹ In children, pre-procedural anxiety has been found to be a function of numerous factors, including: caregiver anxiety, temperament, age, previous medical encounters, a fear of separation from parents, unfamiliar environments, a loss of control, as well as coping with unfamiliar routines, instruments, and procedures.¹

The issue of pre-procedural anxiety is critically important because it not only impacts patient experience and is associated with psychological and physiological distress, but it can affect the efficiency of medical procedures, length of stay in the hospital (LoS), and resource utilization – all of which have economics impacts to both families and the health

system. During medical imaging procedures specifically, anxiety can cause non-compliance or unintentional movement which often leads to failure to complete the procedure or poor image quality, necessitating multiple attempts or the use of sedation to achieve the desired quality of imaging. The impact of sedating a patient has several downstream effects, including the increased potential for adverse events, as well as the need for specialized clinical staff (i.e. Anesthesiologists, Post-Anesthetic Care Nurses, etc.), medications, and lengthier post-procedural monitoring. Studies have also indicated an increase in negative post-procedural outcomes when patients are sedated, such as increased pain perception, increased pharmaceutical consumption, reductions in sleep and eating, generalized anxiety, and greater dissatisfaction.²⁻⁸

Child Life Magnetic Resonance Imaging (MRI) Simulations

The literature suggests that approximately 50-to-75% of all patients who undergo MRI exams at pediatric hospitals are sedated.⁹ CLS reduce sedation rates by exposing pediatric patients to MRI simulations, thus alleviating symptoms of pre-procedural anxiety and distress. MRI simulations include mock scans that appear and sound identical to the real MRI, but lack the magnet, and thus functionality to take images. It's suggested that preparation programs like this can reduce sedation rates by about 20% (those who are eligible, recruited, and successful).⁹

Between November 2017 and January 2019, approximately 377 of the pediatric patients attending BCCH for MRI were eligible and referred for preparation with a CLS. Of the patients who proceeded with simulation (N=344), 82% were able to successfully be converted to a non-sedated MRI (**Table 2**).

Table 2. Simulation statistics from BC Children's Hospital (BCCH) Child Life Department, Nov2017 – Jan2019.

	Non-Sedated MRI	Sedated MRI
Passed Simulator	283	8
Failed Simulator	0	53
TOTAL	283	61

It is evident from the literature and our own hospital data that CLS preparation is effective in reducing anxiety, non-compliant behaviors, and sedation rates.⁹ At BCCH, children under the age of 7 who wish to have a non-sedated MRI must pass an MRI simulator with a CLS. However, the patient's ability to prepare with a CLS can be impacted by geographical barriers and socioeconomic status. Transportation barriers have been repeatedly identified in the literature and by parents as a source of unmet health needs for children in both rural and inner-city populations.¹⁰ This is significant, because if a caregiver cannot get their child to the MRI simulation, they miss the opportunity for a non-sedated MRI, and consequently that increases resources and the risk for complications.

How can digital intervention help to improve access?

Given the effectiveness of CLS preparation programs on the success of non-sedated MRI⁹ and the promising evidence that immersive technologies can effectively reduce pre-procedural anxiety and non-compliant behaviors,^{11,12,21,13-20} we sought to make quality improvements and adjustments to the MRI experience by developing and evaluating a multisensory, realistic, and vivid virtual preparation program. Immersive VR experiences create a three-dimensional image that appears to surround the user. Complimented by high visual and sound quality, motion sensors, and speech recognition, VR can take input from users to interact with a highly realistic and vivid virtual environment. As such, our virtual MRI preparation program has the capacity to expose patients to experiences that mimic medical imaging procedures without the financial and physical limitations associated with traditional in-person simulation. Finding effective solutions for patients with geographical barriers and lower socioeconomic status are worthwhile in reducing sedation rates, increasing cost-savings and improving hospital efficiency.

Project Purpose

The goal is to improve access to effective preparatory resources for non-sedated MRI. Before initiating this project, we conducted a literature review to identify the existing evidence that supports the potential benefits and risks of immersive technologies used for preparation of medical procedures in general. Further, to help discover where and how the program could work, we developed an alpha prototype (V0.1) of the MRI environment. From these tasks, we observed the basic principles of developing a virtual simulation program for medical procedures, of which will inform this project.

This project plan focuses on outlining the procedures for:

1. Developing a VR simulation of the MRI experience at BCCH; and
2. Evaluating the effectiveness of the VR simulation in preparing patients for a **simulated** MRI experience; and
3. Modelling the costs and benefits associated with VR as compared to current programs, to estimate the impact and overall cost-benefit of this new intervention.

4.0 Methods

4.1 Key Question(s)

1. Can a virtual reality simulation effectively prepare children for a non-sedated MRI?
2. What are the economic and performance impacts of integrating this innovation into clinical operations? (at the hospital and health-systems level).
3. What are the estimated socioeconomic benefits to patients and families of this innovation, in comparison to the status quo model?

4.2 Objectives and Hypotheses

Phase 1: Design and Development of the Virtual Reality Experience

1. Work with an interdisciplinary team to collaboratively develop an engaging prototype (V1.0) that models the MRI environment and experience at BCCH.

Phase 2: Technology Evaluation and Comparative Assessment

2. Evaluate the effectiveness in pre-procedural preparation through a comparative assessment against other modes of delivery currently offered at BCCH – including pre-procedural instructional booklet, and mock MRI with CLS.
 - a. *Hypothesis:* There will be differences in outcomes between the virtual reality group and the booklet group.
 - b. *Hypothesis:* There will be no difference in outcomes between the mock MRI and virtual reality simulation groups.
 - c. *Hypothesis:* Children will prefer the virtual reality and simulation exercises to booklet preparation.

Phase 3: Economic Evaluation and Impact Modeling

3. Evaluate costs and benefits of the VR solution and status quo; and conduct economic modelling on the prospective impact of operational integration.

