A minimum of 93 participants (31 participants per group) aged 4-to-13 will be recruited through convenience sampling, consented, and randomized by staff to one-of-three preparation programs (VR, mock MRI, or booklet). Details of the comparison groups are outlined in **Table 4**. Given the restricted availability of the simulator, child life specialists, and the availability of participants, we are unable to fully randomly allocate participants. As such, participants will be randomly assigned to the intervention options available according to their individual availability (using Research Randomizer <https://www.randomizer.org/>). For example, if a participant is available on a Thursday that virtual reality and booklet are available, they will be randomly allocated to one of these interventions.

This phase will have open recruitment to all children and adolescents interested in participating, such that participants may not be BCCH patients scheduled for an MRI. This recruitment strategy was selected due to the resource constraints associated with limiting the evaluation group to MRI patients only.

Table 4. Details of the comparison groups.

	VR Simulation	MRI Preparation Booklet	Mock MRI
Facilitator	Research Assistant	Research Assistant	Child Life Specialist
Location	BCCH	BCCH	Simulation Room
Content	Refer to The Virtual Reality Simulation	Refer to MRI Preparation Book	Individualized intervention in physical simulator.

The different interventions will be held in separate private rooms located in BCCH, such that the VR and booklet groups will not have prior exposure to the imaging centre or the simulation room in advance of their assessment. This is to simulate our intended delivery in hospital, medical office, or clinic settings but minimize alternative explanations associated with testing in the simulation room where assessments will take place (previously described in **Table 3**).

Data will be collected throughout the implementation process (**Figure 3**). The predictive variables (demographics and relevant history, and delivery type) will be captured at the start of the session. The primary outcome variable is likelihood of success (pass/fail) of the MRI simulation, and will be measured at the end of the assessment. Anxiety will also be measured at three time points. Usability testing will be conducted throughout to capture possible quality improvements and amendments to each of the program delivery modes.

Inclusion/Exclusion Criteria

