- 9) Participants will be informed that they will now be completing a simulation test with the MRI scanner. Participants will be reminded of their free and informed ongoing consent.
- 10) The participant will be transferred to the simulation room, located in the medical imaging center at BCCH. Upon entering the simulation room, participants will verbally complete the VPT with staff (during test). In parallel, parents will complete the Short STAI on the iPad. (5 minutes)
- 11) Participants will be guided through a mock MRI and be assessed using MoTrack®, an objective head motion tracking system.³² The simulation will be completed over 20 minutes and will involve progression through the “MRI procedure”, remaining in the bore for 8 minutes. All participants will receive the same type of simulated scan. We will not be simulating any invasive procedures that can sometimes occur during the MRI (i.e. an IV or intravenous contrast liquid). Please note that this assessment involves a mock procedure using the simulator, not a real MRI.
- 12) Immediately following the simulation, participants will verbally complete the VPT with staff (post-test). In parallel, parents will complete the Short STAI on the iPad. (10 minutes).

- 13) Users will be asked to indicate on the *Smileyometer* how they thought the preparation activity was overall in preparing them for the MRI. Parents/guardians will be asked to complete the USE Questionnaire.
- 14) Staff will ask the user open-ended questions on the preparation materials according to three separate criteria of fun, ease of use, and how good it was for learning about the MRI experience. The final usability assessment will take a total of 10 minutes.
- 15) After the session is "complete", children will be told that they "happen to have some time left" so they can play with any of the preparation materials offered (VR, Mock MRI, Booklet) for 5-minutes if they want to "because they did so well during the activity." This will give children a natural choice selection and will be used to gauge preferences for the activities.
- 16) A verbal session debrief will include an opportunity for questions to mitigate any residual feelings of discomfort or anxiety that may arise from the project's activities.

Outcome Measures

The measures used to evaluate the intended outputs and outcomes associated with this project are outlined below (**Table 4**).

Table 4. Outputs and outcomes associated with the project.

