The predictive success in avoiding sedation will be measured using Motrak® software assessment. MoTrak® uses a sensor attached to the participant's head to determine the position of the head in space relative to a transmitter located within the simulator. The sensor records angular rotations as well as positional displacements from an initially calibrated position. This information is displayed and logged by the program in real-time, allowing objective observation of head motion in an MRI simulator.³² The fail threshold is set at 3mm of movement in any of the positional displacements (x,y,z), which is in accordance with imaging protocols at the Hospital.

Child Anxiety: Venham Picture Test – 5 minutes

Anxiety assessment with children will be completed in pictorial form to better adapt to the cognitive and communicative abilities and styles of younger children. The Venham Picture Test has been well-validated in children for assessing procedural anxiety^{33,34}, and comprises eight cards which two figures on each card, one anxious character and one non-anxious character. The children will be asked to point at the figure they feel most like at that moment. All cards will be shown in their number order. If the child points at the anxious figure, a score of one is recorded and if the child points at the non-anxious character, they will be given a score of zero. Children will complete the at three timepoints (before, during, after the mock MRI).

Secondary Measures

Parental Anxiety: Short State-Trait Anxiety Inventory (Short STAI) – 5 minutes

Anxiety assessment with parents/guardians and children at baseline, after completing the intervention, and before the mock MRI. The Short STAI is a 6-item, adapted version of the well-validated Spielberger State-Trait Anxiety Inventory Scale.³⁵ It distinguishes between general proneness to anxious behavior rooted in the personality and anxiety connected to a current state, and has been validated for use in children.³⁵

Demographics and Relevant History

Demographic and possible confounding information (age, sex, prior experience with medical imaging, experience with virtual reality, type of mobile phone) will be obtained through a data collection form. Data will be de-identified using a participant identification number.

Length of Stay (LoS)

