A priori power analysis was calculated using G-Power.³⁸ A total sample size (N) of 93 was calculated to be needed across the 3 groups (31 per group), with a significance level of 95% ($\alpha=0.05$) and a power of 90% ($\beta=0.10$), allowing for a 10% drop out rate. An effect size of 0.2 was selected to reflect the research suggesting that CLS preparation can reduce sedation rates by 20%.

Descriptive analysis will be conducted on the demographics and relevant history data.

Differences in predictive success of the MRI simulation ranking scores (pass or fail) will be examined using a Repeated Measures ANOVA, within-between interaction for three timepoint measurements (before, during, after) of anxiety and delivery type (VR, mock MRI, booklet). In the case of an off-normal distribution, non-parametric tests may be used. Multivariate analysis will test for possible confounding effects (demographics and relevant history).

Survey data (USE questionnaire, Smileyometer) will be analyzed using means and standard deviations of all respondents for each category of the questionnaires. The proportions of the participants reporting high, medium, or low levels will also be calculated.

Study staff will document responses to the guided survey and read the recorded answers back to participants to verify accuracy and elicit possible further reflection. All of the qualitative data will be uploaded to NVivo by study staff. When complete, study staff will code the information to identify major themes, gaps, barriers within the existing approach and the team will devise recommendations for improving the preparation programs. The phases of this process include:

- Familiarizing yourself with the data

- Generating initial codes
- Searching for themes
- Reviewing themes
- Defining and naming the themes
- Triangulation with other findings and producing a report

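### Hypothesis 2b predicts no difference between VR and mock MRI, but the plan has no contrast, margin or interval by which to judge it

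*Combined protocol and SAP*

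**What the plan says.** Section 4.2 lists three hypotheses under Objective 2. The second, 2b, reads: "There will be no difference in outcomes between the mock MRI and virtual reality simulation groups". It is two-sided and worded as a positive prediction.

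The inferential analysis is under Analysis and Interpretation in section 4.4. Pass/fail is to be examined by a "Repeated Measures ANOVA, within-between interaction for three timepoint measurements (before, during, after) of anxiety and delivery type (VR, mock MRI, booklet". There is one fallback: "In the case of an off-normal distribution, non-parametric tests may be used". A multivariate analysis then checks for confounding by demographics and history. Questionnaire data are summarised descriptively.

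On size, section 4.4 says: "A minimum of 93 participants (31 participants per group) aged 4-to-13 will be recruited". The power statement uses one effect size of 0.2, a 5% significance level, 90% power and a 10% drop-out allowance. On allocation: "participants will be randomly assigned to the intervention options available according to their individual availability".

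The outcome is pass/fail on head motion in a mock scan: "The fail threshold is set at 3mm of movement in any of the positional displacements (x,y,z". The mock MRI arm's preparation is described as "Individualized intervention in physical simulator". The assessment, for every arm, is described in step 11 of the Implementation Plan: "Participants will be guided through a mock MRI and be assessed using" the motion tracker.

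**The concern.** A hypothesis of no difference cannot be supported by failing to reject a test for a difference. It needs an estimate of the specific contrast, with an interval narrow enough to exclude differences that matter. The plan has neither.

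The three-group interaction cannot settle 2b either way. If significant, it does not say which groups differ. If not, the cause may be similarity or too few data. The 0.2 in the power statement is a difference to detect, not a margin.

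Mock MRI with a Child Life Specialist is a named comparator in Objective 2, and 2b is the only hypothesis that sets VR against it. With no rule fixed beforehand, the judgement on 2b would be made after the data are seen. Phase 3 (section 4.5) also takes its effects from Phase 2 and divides cost differences by effect differences. An estimate with an interval can be used there; a bare statement of no difference cannot.

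**Working it through.** **The plan's own figure.** The stated total is 93 (31 per group). For a repeated-measures ANOVA within-between interaction with f = 0.2, three groups, three time points, 5% level, 90% power, correlation 0.5 and no sphericity correction, the total needed is 67, or 69 in equal groups. After 10% drop-out it is 69/0.9 = 77. A total of 93–94 appears only under settings that the plan does not state, such as a correlation of about 0.37–0.38, a sphericity factor of 0.75, or two time points. The 93 can therefore be neither confirmed nor called wrong, and the present point does not depend on it.

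**Inputs for the illustration.**
- Per arm: 31 planned; 31 × 0.9 = 27.9, so 28 evaluable after drop-out. Equal arms are assumed.
- Mock MRI pass rate p: not given, so assumed at 60%, 82% and 95%. The 82% is borrowed from section 3.0 (283/344 converted to non-sedated MRI among referred patients). That is a different endpoint and population from 3 mm head displacement in volunteers.
- Deficit and margin: 20 points, assumed.
- Test: pairwise two-sided Pearson at 5%, which the plan does not name.

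**1. Chance that a true 20-point VR deficit is non-significant**, and **2. precision at equal rates**. Step 1 is a full binomial enumeration. Step 2 uses half-width = 1.96 × √(2p(1−p)/n); for p = 0.82, n = 28 this is 1.96 × √(0.2952/28) = 20.1 points.

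| Mock MRI pass rate | Non-significant, n = 28 / 31 | Normal half-width (points) | Mean Newcombe half-width (points) |
|---|---|---|---|
| 60% | 69.2% / 62.9% | 25.7 / 24.4 | 23.8 / 22.8 |
| 82% | 60.8% / 57.6% | 20.1 / 19.1 | 20.1 / 19.1 |
| 95% | 39.9% / 35.2% | 11.4 / 10.9 | 15.1 / 14.1 |

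**3. Chance of meeting a 20-point margin when the rates are truly equal** (enumeration, Newcombe interval, n = 28 / 31).

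| Pass rate | 95% CI within ±20 | 90% CI within ±20 | Lower 95% limit above −20 |
|---|---|---|---|
| 60% | 0% / 0% | 2.0% / 9.1% | 35.4% / 39.2% |
| 82% | 6.1% / 11.3% | 21.1% / 30.0% | 48.9% / 54.1% |
| 95% | 59.7% / 62.2% | 78.1% / 83.3% | 79.8% / 81.1% |

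**4. Evaluable children per arm for a 20-point margin, 90% power, equal rates** (normal approximation).
- Non-inferiority: (1.960 + 1.282)² × 2p(1−p)/0.04 = 127, 78 and 25 at 60%, 82% and 95%.
- Equivalence by 95% CI: (1.960 + 1.645)² × 2p(1−p)/0.04 = 156, 96 and 31. By 90% CI: 130, 80 and 26.
- The approximation is optimistic at 95%. Step 3 shows only 80–81% for non-inferiority with 28–31 per arm.
- Narrower margins cost more. At 82.3% (283/344), non-inferiority needs 307, 137 or 77 per arm for margins of 10, 15 or 20 points.

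**5. Anxiety.** The 95% half-width for VR minus mock MRI, adjusted for the pre-test score, is t × √(2(1−r²)/n) in SD units. The pre-test correlation r is not given. At n = 28 / 31 the half-width is 0.536 / 0.508 for r = 0, 0.464 / 0.440 for r = 0.5, and 0.383 / 0.363 for r = 0.7.

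**The case against.** The strongest reply is that this is a development project in plan-do-study-act cycles, with VR meant to complement Child Life Specialists. Its 2b is one of three short expectations. The plan never uses the words equivalence or non-inferiority, and never says that a non-significant result would confirm 2b. This limits the stakes, and VR versus booklet (2a) may matter more for children who cannot attend. It does not remove the gap: the project states hypotheses, randomises and reports a power calculation, yet gives no rule for this hypothesis. Estimation suits exploratory work.

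Several narrower points stand:
- No pairwise contrast is named for 2a either. Only the missing rule for no difference is particular to 2b.
- The same paragraph assigns the pass/fail outcome to an ANOVA whose repeated measure is anxiety. That is a separate problem, and a pass-rate contrast does not cure it.
- Section 4.5 does not name mock MRI as the control for the cost-effectiveness ratio, so the Phase 3 consequence is indirect.
- The magnitude rests on an assumed pass rate and one assumed margin, and the equivalence result is kinder with a 90% interval.

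None of these supplies a contrast, margin or interval for 2b.

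**Conclusion.** The concern holds. The hypothesis and the method do not match: 2b asserts similarity, and the plan contains only tests for difference, with no VR-versus-mock MRI contrast and no criterion. That conclusion follows from the text and needs no assumed pass rate.

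The size does depend on assumptions (pass rate, 20-point deficit or margin, equal arms, pairwise test). On those, non-significance would often hide a 20-point deficit, and a parity claim by 95% interval would usually fail at pass rates of 60% or 82% even if the arms were identical. Near 95% it becomes possible, but is not assured. This should be fixed before analysis; it does not by itself undermine the trial.

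**What to change.** **Main change: estimation.** Replace 2b with wording such as: *We will estimate the VR minus mock MRI difference in MoTrak pass rate, and in anxiety adjusted for the pre-test score, with 95% confidence intervals. A p-value above 0.05 will not be taken as support for no difference, and no parity claim will be made from it.* Add the contrast to Analysis and Interpretation in section 4.4. Name the anxiety scale (child Venham test, parent Short STAI, or both) and the later time point. State that precision is limited and that allocation was random only among the options open to each child.

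The cost is one reworded hypothesis and two or three sentences, with no extra participants. The price is that no verdict of similarity is given.

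**Only if a parity claim is wanted:**
1. Fix and justify a margin before analysis.
2. Say whether the claim is equivalence (two-sided, as 2b is worded) or non-inferiority, which changes the hypothesis.
3. In justifying the margin, allow for the fact that the mock MRI arm prepares in a physical simulator and the outcome is measured in a mock MRI.
4. Report the result as inconclusive if the interval does not clear the margin.

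This option costs more: the planned 28–31 evaluable per arm is probably too few unless pass rates are near 95%, and may fall short even there.

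### Hypotheses 2a (VR versus booklet) and 2b (VR versus mock MRI) have no order or condition, so the plan does not say which of them answers key question 1

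*Combined protocol and SAP*

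**What the plan says.** Key question 1 (section 4.1) is "Can a virtual reality simulation effectively prepare children for a non-sedated MRI". Section 4.2 gives two Phase 2 hypotheses on outcomes that bear on it. Hypothesis 2a is "There will be differences in outcomes between the virtual reality group and the booklet group", with no direction. Hypothesis 2b is "There will be no difference in outcomes between the mock MRI and virtual reality simulation groups", with no margin. Hypothesis 2c concerns preference. None is named primary, ranked or made conditional on another.

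Section 4.4 states that "The primary outcome variable is likelihood of success (pass/fail) of the MRI simulation". Its Analysis and Interpretation text, the only Phase 2 analysis plan, names one model: a "Repeated Measures ANOVA, within-between interaction for three timepoint measurements (before, during, after) of anxiety and delivery type (VR, mock MRI, booklet"), plus an unspecified multivariate check for confounders. It gives no VR-booklet or VR-mock contrast, no testing order, no rule for upholding 2b and no equivalence or non-inferiority margin.

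All three arms receive a preparation, and the booklet is the standard one. Mock MRI versus booklet is not a stated outcome hypothesis. Recruitment is open, so that "participants may not be BCCH patients scheduled for an MRI".

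**The concern.** Showing that VR does not differ from mock MRI supports the effectiveness of VR only if mock MRI is itself effective in this sample, under this test. No stated comparison establishes that. The two hypotheses can therefore point in different directions: VR fails to separate from the booklet and also fails to separate from mock MRI. The plan does not say how to read that result, so the answer to key question 1 would depend on which hypothesis is put first once the data are known.

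At stake is a conclusion that a self-guided VR tool can stand in for preparation led by a Child Life Specialist, drawn from a trial in which VR was not shown to beat a booklet.

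**Working it through.** **The plan's own figure.** The plan gives N = 93 (31 per group), alpha 0.05, power 90%, effect size 0.2 and 10% dropout. Take 0.2 as Cohen's f for the repeated-measures interaction, with noncentrality f² × N × m / (1 − rho), where m is the number of timepoints. Rho is not stated.
- Three timepoints, rho 0.5: N = 69, or 77 after dropout. This does not reproduce 93.
- Three timepoints with rho 0.37-0.38, or two timepoints with rho 0.5: N = 84. Then 84 × 1.1 = 92.4, rounded up to 93 (84 / 0.9 gives 94).

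So 93 is reachable as a sample size for an interaction on a repeated measure. One-way ANOVA, chi-square and 20-point two-proportion formulas do not give it (246 or more in total). It was not derived for 2a or 2b on pass/fail.

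**Inputs for the check.** Per-arm n is 31 as planned, or 31 × 0.9 = 27.9, about 28, after dropout. Pass rates are assumptions. Equal arms are taken over 0.60-0.90, which covers the historical 283/344 = 82%. The 20-point scenarios mirror the plan's 20% figure, read as percentage points. Each pair is tested at two-sided 0.05 with z = (p1 − p2) / sqrt(2 × pbar × (1 − pbar) / n). 2b counts as upheld when VR versus mock MRI is not significant. Probabilities are summed exactly over the three binomial arms, for n = 28 and 31.

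| True pass rates, VR / mock / booklet (assumed) | 2b upheld | 2b upheld, 2a not significant | 2b upheld, 2a significant in favour of VR |
|---|---|---|---|
| All equal, 0.60 to 0.90 | 0.945-0.952 | 0.90-0.91 | about 0.02 |
| 0.62 / 0.82 / 0.62 | 0.58-0.61 | 0.55-0.58 | about 0.02 |
| 0.82 / 0.82 / 0.62 | 0.95 | 0.55-0.58 | 0.37-0.40 |

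Row 1 is what one expects: 1 − 0.05 = 0.95 for one test, and roughly 0.95 × 0.95 = 0.90 for two, slightly higher because the VR arm is shared. With Fisher's test the first entry is 0.97-0.99.

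Row 2 follows from low pairwise power. At n = 31, with mean rate 0.72, the normal approximation gives (0.20 − 1.96 × sqrt(2 × 0.72 × 0.28 / 31)) / sqrt((0.82 × 0.18 + 0.62 × 0.38) / 31) = (0.200 − 0.224) / 0.111 = −0.21, so power is about 0.42. At n = 28 it is about 0.38. The exact values are 0.42 and 0.39, and 1 minus these gives 0.58-0.61.

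**Would a margin alone settle it?** The 95% CI half-width for VR minus mock MRI at 0.82 is 1.96 × sqrt(2 × 0.82 × 0.18 / 31) = 0.19. With equal arms between 0.2 and 0.82 and n = 31, a lower limit above −20 points is met in about 35-56% of trials, and above −10 points in about 13-18%. If VR must also first beat the booklet, both fall to about 1-2.5%. The margins are assumptions.

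**The case against.** **2b is true when the arms are equal.** Upholding it is then not an error, and the 95% is simply 1 − alpha. This stands. The problem lies in the further step from 2b to effectiveness, which the plan neither licenses nor rules out.

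**Equal arms do not mean that nothing works.** A reader might infer that 2b would be confirmed when no preparation works. The documents do not support that. The booklet is an active standard preparation, so equal pass rates may mean that all three work. What holds is that the design cannot separate the two cases.

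**The plan has grounds for trusting mock MRI.** Section 3.0 reports 82% conversion to non-sedated MRI and says the effectiveness of Child Life preparation is evident. But Table 2 covers referred MRI patients and has no booklet comparator. It does not show that an 8-minute simulated scan in openly recruited volunteers can detect a preparation effect.

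**All three arms enter the planned model.** True, but it is built around the anxiety timepoints and names no contrast on pass/fail.

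**A failed 2a would be reported too.** Probably. That the trial would announce VR as equal to mock MRI is an inference. What is missing is a rule set in advance for reading the two results together.

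**Phase 3 would go wrong.** A reader might infer that ordering the hypotheses changes the economic inputs. It does not. Section 4.5 builds its cost-effectiveness ratios on differences in effect, not on hypothesis verdicts, so the same estimates enter either way.

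**A strict condition blocks correct conclusions, and a tight margin already removes much of the problem.** Both are partly right. The power cost is real and belongs in the plan. A margin helps, but does not say which comparison decides key question 1.

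**Conclusion.** The concern holds in this form: the plan gives two outcome hypotheses bearing on key question 1, does not say which decides, and has no rule for reading them when they disagree. Under equal arms that disagreement is the expected result (about 90% of trials). If VR only matches the booklet and mock MRI is 20 points better, 2b is still upheld in 58-61%. Making 2b depend on a VR-favouring result against the booklet lowers both to about 2%.

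These figures assume 28-31 per arm, the pass rates shown, and 2b judged by non-significance. The documents state no other rule, and the wording of 2b invites that one. This should be corrected. It sits beside the missing margin for 2b and the lack of a named pass/fail analysis, and does not replace either.

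**What to change.** In section 4.2 and in Analysis and Interpretation (section 4.4), state that:

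1. VR versus booklet on pass/fail, two-sided 0.05 and in favour of VR, is the comparison that decides key question 1. The direction matters: as worded, VR worse than the booklet would satisfy 2a.
2. VR versus mock MRI is reported as a difference in pass rates with a 95% CI. Non-significance is not read as 'as good as'. That wording is allowed only if step 1 favours VR and a margin fixed in advance is met; otherwise the comparison is descriptive.
3. Mock MRI versus booklet is reported with a 95% CI as the check that the test can detect a preparation effect. Two limits should be noted: children in the mock arm prepare in the simulator itself, and allocation depends on availability.

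This takes a few sentences and no extra data, and a fixed sequence costs no alpha. The price, which the plan should state, is power. At 28-31 per arm, step 1 has about 39-42% power for 0.82 versus 0.62. If VR and mock MRI both truly beat the booklet by 20 points, step 1 succeeds with a non-significant 2b in only about 37-40% of trials, and requiring a margin lowers this further. The check in item 3 has the same 39-42% power, so an interval that includes zero there would be inconclusive.
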